### *Statistical Analysis Plan*

*Analyses:* All analyses were carried out in SPSS V29.0.1.1. First, independent sample ttests were used to assess for differences in demographic and clinical variables between those who downloaded their assigned app and enrolled in the trial and those who did not, as well as between the two enrolled groups at baseline, and to compare the baseline scores of treatment completers versus individuals who dropped out of the study and failed to supply follow-up data at post-treatment.

Next, change over time both within group and between groups was examined. Analyses were completed using both per protocol (completer) and intention-to-treat (ITT) (sensitivity analysis) approaches using multiple imputation to estimate missing data. Per protocol analyses only included individuals who completed the post-treatment follow-up questionnaires. ITT (which accounts for that missing data) is generally considered the gold standard in clinical trials, especially longitudinal randomized controlled trial with missing data due to attrition [48], although it has also been criticized for being overly conservative, and for confounding the issues of acceptability and efficacy [49]. We conducted sensitivity analyses using multiple imputation to account for missing data at post-test, the only time point at which between group comparisons were possible. Because the data were missing not at random (MNAR) we used a monotone

imputation with linear regression and 5 iterations. We then analyzed the pooled data using multivariate and univariate analysis of covariance, as well as within group paired sample t-tests.

Initially, paired sample t-tests were used to examine within group change from baseline to immediate post-treatment for each group and to examine maintenance of gains from post CBT treatment to 3- and 6-months follow-up. Subsequently, multivariate and univariate general linear models were used to examine between group effects at post treatment (8 weeks), controlling for baseline levels of the dependent variables.

With respect to between group differences, we first conducted a conservative MANCOVA predicting all outcome measures (dependent variables GSRS, IBSQoL, VSI, GICog, FFQ, BDI) from the independent variable condition, controlling for all of those same measures at baseline. We then ran a series of ANCOVAs predicting each of the outcome measures individually at post-treatment from condition controlling for that measure's baseline value.

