With respect to clinically significant change, we used Jacobsen and Truax's Criterion B (falling within 2 SD of the healthy mean), which is more conservative than Criterion A (falling 2 SD below the pathological mean) [50]. With respect to effect sizes, we report on partial eta squared ( $\eta^2$ ), Cohen's  $d$ , and the pooled pretest standard deviation for weighting the differences of the pre-post-means ( $d_{ppc2}$ ) [51]. The  $d_{ppc2}$  measure is designed for pre-post controlled trials where the sample sizes may be uneven across groups, as was the case in our data set.

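### As worded, the SAP pools the multiply imputed data before analysing them; done literally, this loses the between-imputation variance in the ITT sensitivity analysis

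*SAP*

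**What the plan says.** The SAP (Statistical Analysis Plan, Analyses) sets out two approaches: "Analyses were completed using both per protocol (completer) and intention-to-treat (ITT) (sensitivity analysis) approaches using multiple imputation to estimate missing data". Imputation is confined to one visit: "We conducted sensitivity analyses using multiple imputation to account for missing data at post-test, the only time point at which between group comparisons were possible". The method is introduced with "Because the data were missing not at random (MNAR) we used a monotone" and continues as "imputation with linear regression and 5 iterations". The next sentence gives the analysis step: "We then analyzed the pooled data using multivariate and univariate analysis of covariance, as well as within group paired sample t-tests". The univariate models are ANCOVAs "predicting each of the outcome measures individually at post-treatment from condition controlling for that measure's baseline value".

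Nothing elsewhere in the SAP changes the order of these steps. It does not say that each imputed set is analysed on its own, names no combining rule, and does not say how a multivariate test is obtained across sets. The number of imputed sets is not given separately from the 5 iterations, and the variables in the imputation model are not listed. No sample size or attrition figure appears.

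**The concern.** Multiple imputation works in a fixed order: impute several times, analyse each completed set, then combine the estimates and their variances. The combining step is where uncertainty about the missing values enters the standard error, through the spread of the estimates between sets. The sentence in the SAP reverses the last two steps. If the sets are merged into one file before the model is fitted, the software sees one complete data set and treats every imputed value as if it had been observed.

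The completer analysis leaves out everyone without post-treatment questionnaires. The imputed analysis is therefore the only between-group analysis that keeps them, and it is the check on the completer result. If its standard errors are too small, it can seem to support a completer finding more firmly than the data allow.

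**Working it through.** The SAP gives no figure to reproduce, so the check asks what each reading of the sentence does to the type I error.

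**Inputs.** From the SAP: ANCOVA of post-treatment score on condition and baseline; linear-regression imputation of post-test values only. Assumed, because the SAP does not state them: two-sided 5% test; m = 5 imputed sets (inferred from the 5 iterations); missing share p from 5% to 50%, equal in both arms and completely at random; condition and baseline in the imputation model unless noted.

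**Formulas.** Set the variance of the condition effect with nothing missing to 1.

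- Using only the observed scores, the variance is 1/(1-p) = 1 + p/(1-p). The within-imputation variance is W = 1 and the between-imputation variance is B = p/(1-p).
- The true variance of the combined estimate (Rubin) is T = W + (1 + 1/m)B = 1 + 1.2p/(1-p).
- If the 5 sets are averaged into one, the imputed scores keep only about one fifth of their residual variance. The software then reports about A = (1-p) + p/5.
- If the 5 sets are stacked, each participant counts five times and the software reports about S = 1/5 = 0.2.
- Null rejection is 2[1 - Φ(1.96·√(R/T))], with R = A or S.

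**Example, 20% missing.** T = 1 + 1.2 × 0.25 = 1.30.

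- Averaged: A = 0.80 + 0.04 = 0.84; 1.96 × √(0.84/1.30) = 1.576; rejection 11.5%.
- Stacked: 1.96 × √(0.20/1.30) = 0.769; rejection 44%.

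**Example, 50% missing.** T = 1 + 1.2 × 1 = 2.20.

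- Averaged: A = 0.50 + 0.10 = 0.60; 1.96 × √(0.60/2.20) = 1.024; rejection 31%.
- Stacked: 1.96 × √(0.20/2.20) = 0.591; rejection 55%.

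| Missing | T | Averaged, formula | Averaged, simulated | Stacked, formula |
|---|---|---|---|---|
| 5% | 1.063 | 6% | 6-7% | 40% |
| 10% | 1.133 | 8% | 7-8% | 41% |
| 20% | 1.300 | 12% | 11-13% | 44% |
| 30% | 1.514 | 16-17% | 16-18% | 48% |
| 50% | 2.200 | 31% | 29-32% | 55% |

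With nothing missing, stacking already gives 2[1 - Φ(1.96/√5)] = 38%. Most of its inflation comes from counting people five times.

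**Simulation.** Null trials were simulated with total N from 60 to 300, baseline-outcome correlation 0.4 to 0.8, and 2,000 or 4,000 trials per scenario. At 2,000 trials the Monte Carlo standard error is about √(0.05 × 0.95/2000) = 0.5 points near 5%. Stacking rejected 39-45% at 5-20% missing and 54-56% at 50%. Fitting each set and combining by Rubin's rules rejected 4.2-6.0% throughout.

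**Condition left out of the imputation model** (N = 120, correlation 0.6; 20% or 40% missing in both arms, or 50% against 20%). Averaging rejected about 4-5%, stacking 28-33%, and Rubin's rules 0.3-1.2%. Averaging is near nominal here because the imputed scores carry no difference between arms, so the estimated effect shrinks along with its standard error.

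**The case against.** The strongest reply is that the phrase is loose shorthand for results pooled over the imputed sets. The SAP never says that the sets were stacked or averaged, and on the benign reading the error rate is nominal. The document cannot settle this, so a reader who concludes that the ITT analysis does have a type I error several times too large goes further than the text allows.

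Two arguments for that stronger conclusion also fail. One is that a single MANCOVA result can come only from stacked or averaged data. It can also come from a multi-parameter Wald test on the combined condition coefficients. The other is that reporting partial eta squared shows how the sets were handled. The sentence beginning "With respect to effect sizes, we report on partial eta squared" does not tie that measure to the imputed analysis, and it may come from the completers alone.

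It is also fair to say that the inflation is small under averaging with 5-10% missing, and absent under averaging if condition was omitted from the imputation model. Even where averaging inflates the error, most null trials would still not reject, so the analysis would not routinely confirm a false completer finding. The SAP labels the analysis a sensitivity analysis.

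All of this limits how the point can be stated. It does not remove it. The only order of steps that the SAP gives is the wrong one, and following it as written yields invalid standard errors. Even on the benign reading, the SAP does not say how the multivariate test is combined.

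**Conclusion.** The point holds in conditional form. The SAP describes multiple imputation with pooling ahead of analysis, and carried out literally that discards the between-imputation variance. The consequence ranges from none (pooled estimates were meant, or sets averaged without condition in the imputation model), through roughly twice nominal (averaged with condition included, 20% missing), to about 11 times nominal (stacked, 50% missing: 55/5).

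These sizes are illustrations. They rest on an assumed attrition, on 5 imputed sets, and on data missing completely at random, although the SAP asserts that its data are missing not at random. They cover the single-outcome ANCOVA only, not the MANCOVA or the paired t-tests. The defect should be corrected, but it is confined to the ITT sensitivity analysis.

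**What to change.** Replace the sentence on analysing pooled data with wording such as:

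> Each ANCOVA and paired comparison is fitted separately in every imputed data set, with condition and baseline in the imputation model. The adjusted mean difference (or mean change) and its standard error are combined by Rubin's rules with small-sample degrees of freedom.

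In addition:

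- State the number of imputed data sets separately from the number of iterations.
- For the multivariate test, either combine the six condition coefficients and their covariance matrix in a pooled multi-parameter Wald test, or restrict the MANCOVA to observed data and say so.
- Confirm what was actually run. If the sets were stacked or averaged, re-run the ITT sensitivity analysis.

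The cost is one paragraph and, at most, a re-run of existing analyses. If the sets were stacked or averaged, expect wider confidence intervals in the ITT sensitivity analysis. If Rubin's rules were already applied with condition in the imputation model, only the wording changes.

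### Durability at 3 and 6 months rests on paired t-tests alone, with no stated basis for calling gains maintained and no clear handling of missing follow-up scores

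*SAP*

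**What the plan says.** All of this is in the SAP, Statistical Analysis Plan, Analyses.

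- **Test.** For the first step, "paired sample t-tests were used to examine within group change from baseline to immediate post-treatment for each group". The same tests are then used "to examine maintenance of gains from post CBT treatment to 3- and 6-months follow-up". The multivariate and univariate general linear models are confined to post-treatment at 8 weeks. No longitudinal model, interval criterion or maintenance rule is given for 3 or 6 months.
- **Imputation, specific sentence.** The sensitivity analyses use "multiple imputation to account for missing data at post-test, the only time point at which between group comparisons were possible".
- **Imputation, general wording.** An opening sentence says that analyses were done both in completers and by ITT with multiple imputation. A later sentence says that the pooled imputed data were also analysed by within-group paired t-tests. Neither names a visit.
- **Dropout comparison.** Baseline scores of completers are compared with those of "individuals who dropped out of the study and failed to supply follow-up data at post-treatment". The per-protocol set is likewise defined by the post-treatment questionnaires.
- **View of missing data.** The SAP writes that "ITT (which accounts for that missing data) is generally considered the gold standard in clinical trials", especially for longitudinal trials with attrition, and adds that ITT has been criticised as too conservative. On mechanism it writes: "Because the data were missing not at random (MNAR) we used a monotone" imputation.

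**The concern.** Maintenance is a claim of little or no loss. The null hypothesis of a paired t-test is no change, so a non-significant result fits two situations: gains were kept, or there were too few pairs to see the loss. The SAP states nothing else on which a maintenance conclusion would rest.

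The second problem is who is in the test. A paired test needs both scores, and the only visit for which imputation is specifically stated is post-test. People who gave post-CBT data and then left are not covered by the dropout comparison either. If those who stay differ in their post-CBT score, the observed change among stayers is a biased estimate of the change in everyone treated. This holds even when the missingness is fully explained by that observed score (MAR).

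At stake is the durability statement. The randomised comparison at 8 weeks does not depend on it.

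**Working it through.** The SAP gives no follow-up sample size, SD, correlation, retention or margin, so there is no figure of its own to reproduce. The inputs below are all **assumed**: equal SDs at the two visits, set to 1; correlation r between post-CBT and follow-up of 0.4, 0.6 or 0.8; two-sided alpha 0.05.

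**1. Can a non-significant result be told from a real loss?**
SD of change = √(2(1−r)) = 1.095, 0.894, 0.632. For a true loss of 0.25 SD, the standardised loss is 0.25 divided by these: 0.228, 0.280, 0.395. The noncentral t distribution gives the chance of p>0.05. The 95% CI half-width is t(0.975, n−1) × SD of change / √n.

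| Pairs | P(p>0.05), r=0.4 / 0.6 / 0.8 | CI half-width (SD) |
|---|---|---|
| 20 | 0.837 / 0.779 / 0.611 | 0.51 / 0.42 / 0.30 |
| 60 | 0.587 / 0.433 / 0.146 | 0.28 / 0.23 / 0.16 |
| 100 | 0.382 / 0.210 / 0.025 | 0.22 / 0.18 / 0.13 |

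**2. Bias when staying depends on the post-CBT score (MAR).**
Assume a logistic model with log-odds of staying changing by 0.5 per SD of the post-CBT score, and a true mean change of zero. Given a standardised post-CBT score z, the expected change is (r−1)z. The bias is therefore (r−1) times the mean of z among those retained.

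- 60% retained: mean z is 0.189 in size. Bias = 0.6, 0.4, 0.2 × 0.189 = 0.114, 0.076, 0.038 SD.
- 80% retained: mean z is 0.096 in size. Bias = 0.6, 0.4, 0.2 × 0.096 = 0.058, 0.038, 0.019 SD.

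The sign depends on who leaves. In a simulation at 60% retention (four visits, equal correlations, 60 or 100 people entering, 4,000 trials per setting), the complete-pairs mean change was 0.036 to 0.115 SD in size, with 95% CI coverage of 0.88–0.93. Maximum likelihood on all observed visits, with an unstructured covariance, gave −0.005 to 0.003 SD.

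**3. Bias when staying depends on the change itself (MNAR).**
With 60% retained and log-odds 0.5 per SD of the change, bias = 0.189 × SD of change = 0.207, 0.169, 0.120 SD. A model that assumes MAR does not remove this.

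**4. Effect of a shift in the missing values.**
Movement of the mean change = shift × share missing. With 40% missing and a shift of 0.25 SD: 0.25 × 0.40 = 0.10 SD.

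**5. Which follow-up scores enter the tests?**
The general completer/ITT sentence and the imputed paired t-tests could be read as covering all visits. The specific sentence limits imputation to post-test and gives as its reason that only there can groups be compared. That reason does not extend to within-group tests at 3 and 6 months. At most, an imputed post-test score could enter a pair; the follow-up score would still have to be observed. Complete pairs is thus the likelier reading, but an inference.

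**The case against.** The strongest case against has five parts.

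- **The SAP never says that p>0.05 means maintained.** This stands. A reader might infer that rule from the word maintenance, but the text only says that it is examined. A paired t-test also yields a mean change and interval, and a significant further improvement would support maintenance among those observed. What remains is that the SAP states no basis for the conclusion.
- **Complete pairs is not stated.** This stands in part. The two sentences that name no visit leave room for imputation at follow-up, and it would be too strong to say the SAP excludes it.
- **The gold-standard and MNAR remarks do not concern follow-up.** Largely right. The first is qualified in its own sentence, and the second directly follows the sentence on missing post-test data. A reader might infer that the SAP breaks a rule it set for itself; the text does not go that far. The remarks show only that the SAP treats attrition as important and does not carry this clearly to 3 and 6 months.
- **A mixed model assumes MAR, and its gain is modest.** True. The bias in step 2 is smaller than the CI half-width even with 100 pairs (0.114 against 0.22 SD at r=0.4; 0.038 against 0.13 SD at r=0.8). But this bias does not shrink as numbers grow, and the MNAR case is why a separate sensitivity analysis belongs beside the model.
- **Without a margin, an interval sets no criterion either.** It gives no yes/no verdict, but it does say how large a loss the data rule out, which a non-significant p-value does not.

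**Conclusion.** The point holds as an improvement that should be made. Paired t-tests are the only analysis named for maintenance, they do not by themselves support a conclusion that gains were kept, and missing 3- and 6-month scores are most likely left out of the tests.

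Its size cannot be known from the SAP. Under the assumed inputs, the chance of overlooking a 0.25 SD loss runs from 2.5% to 84% between 100 and 20 pairs, and the 0.25 SD itself is an illustration, not a justified threshold. The MAR bias is 0.02–0.11 SD between 80% and 60% retention. The concern is large if follow-up is small or selective, and modest otherwise.

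A reader might infer that the trial's main result is in doubt, or that the maintenance claim is false. Neither follows: only the secondary, uncontrolled within-group statement is affected, and the documents give no data showing that gains were lost.

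**What to change.** For each outcome, in CBT-treated participants:

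1. Replace the follow-up paired t-tests with a linear mixed model over pre-CBT, post-CBT, 3 and 6 months, using everyone with any data. Treat visit as categorical, use an unstructured covariance, and state a simpler fallback in case it does not converge.
2. Report the changes from post-CBT to 3 months and from post-CBT to 6 months with 95% CIs, and the number observed at each visit.
3. Base the maintenance statement on the estimate and on how large a loss its interval excludes, not on p>0.05. Call it uncontrolled within-group change. A formal loss margin is optional and should be labelled post hoc if results are already known.
4. Because the model assumes MAR and the SAP calls its data MNAR, add one sensitivity analysis: impute missing 3- and 6-month values, worsen them in steps, and report the shift at which the conclusion changes.
5. As supporting description, compare post-CBT scores of people with and without follow-up data.

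**Cost.** SAP wording, one SPSS MIXED model per outcome and one shifted-imputation analysis, all on existing data and in the software already named. Precision gains little: with 60 people entering and r=0.6, the simulated SD of the estimate was 0.145 against 0.150 for complete pairs, about 3% lower. The benefit is removal of bias under MAR. Wide intervals (half-width 0.30–0.51 SD with 20 pairs) may leave maintenance unconfirmed for some outcomes.

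### Six post-treatment ANCOVAs follow a MANCOVA with no stated dependence on it and no multiplicity adjustment, so claims about single outcomes are not protected against false positives

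*SAP*

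**What the plan says.** The between-group part of the SAP (section Statistical Analysis Plan, under Analyses) has two steps. The first is a joint test: "we first conducted a conservative MANCOVA predicting all outcome measures (dependent variables GSRS, IBSQoL, VSI, GICog, FFQ, BDI"), with all six baseline measures as covariates. The second is a set of single-outcome tests: "We then ran a series of ANCOVAs predicting each of the outcome measures individually at post-treatment from condition", each adjusted for its own baseline.

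The section also introduces these models in general terms: "multivariate and univariate general linear models were used to examine between group effects at post treatment (8 weeks"). It describes post-test as "the only time point at which between group comparisons were possible". The analyses are run on two sets: "Analyses were completed using both per protocol (completer) and intention-to-treat (ITT) (sensitivity analysis) approaches".

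The SAP does not say that the ANCOVAs were run or interpreted only if the MANCOVA was significant, and it gives no adjustment across the six. The closing paragraph covers only clinically significant change and effect sizes.

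**The concern.** Calling the MANCOVA conservative invites the reader to think that it takes care of testing six outcomes. The text gives only an order, first one and then the other, which can be read in two ways:

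- **The MANCOVA is not a gate.** It then does nothing for the error rate of the six ANCOVAs, which are six unadjusted tests.
- **The MANCOVA is a gate.** It then protects against a false positive when nothing differs between the groups. Once a real effect on one outcome opens it, the other outcomes are each tested at the full level.

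The ANCOVAs are the only post-treatment between-group tests of single outcomes that the SAP describes. (It also has between-group t-tests at baseline, but these say nothing about treatment effect.) Any statement that treatment improved a particular measure therefore rests on them, and a reader cannot tell which significant results are protected.

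**Working it through.** The SAP states no error rate of its own, so there is no figure to reproduce.

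**Inputs from the SAP**
- Six outcomes: GSRS, IBSQoL, VSI, GICog, FFQ, BDI.
- One between-group time point, hence six ANCOVAs per analysis set.

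**Assumptions, not in the SAP**
- Two-sided 0.05 per test, so c = 1.96.
- Equal correlation r between the test statistics, shown over a range.
- For the gated reading, the size of the real effect, given as a shift in the z statistic.

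**Step 1. No gate, k true nulls.** At r = 0 the chance of any false positive is 1 − 0.95^k. For k = 6 this is 1 − 0.95^6 = 0.265. For r > 0, with equicorrelated normal statistics, it is

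1 − ∫ φ(u) · [Φ((c − √r·u)/√(1 − r)) − Φ((−c − √r·u)/√(1 − r))]^k du.

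| r | 0 | 0.3 | 0.5 | 0.7 | 0.9 | 0.95 |
|---|---|---|---|---|---|---|
| six true nulls, no gate | 26.5% | 24.1% | 20.7% | 16.4% | 10.8% | 8.9% |

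**Step 2. MANCOVA as a gate, all six null.** I approximated the gate by a large-sample omnibus chi-square test with 6 degrees of freedom at 0.05, followed by the six tests at 0.05. The risk of any false positive is 4.9% (r = 0), 4.0% (0.5), 3.3% (0.7) and 1.9% (0.95). The gate works here.

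**Step 3. MANCOVA as a gate, one real effect and five nulls.** The risk among the five nulls depends on how often the real effect opens the gate.

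| z-shift of the real effect | r = 0 | r = 0.5 | r = 0.7 |
|---|---|---|---|
| 0.5 | 5.0% | 4.3% | 4.0% |
| 2 | 12.6% | 13.4% | 13.2% |
| 2.8 | 17.8% | 17.0% | 14.8% |
| large-effect limit | 22.6% | 18.3% | 14.8% |

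The limit is the step 1 formula with k = 5, since the gate is then always open. At r = 0 it is 1 − 0.95^5 = 0.226.

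**Step 4. More than one real effect, large-effect limits.** With 2, 3, 4 and 5 real effects, the limits are 18.5, 14.3, 9.8 and 5.0% at r = 0. At r = 0.7 they are 13.0, 10.9, 8.4 and 5.0%. With only one null left, the risk cannot exceed the level of a single test.

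**Step 5. Do the differing covariates matter?** The MANCOVA adjusts for all six baselines and each ANCOVA for its own only. I simulated these models with an assumed 50 per group, a pre-post correlation of 0.6 and 8,000 trials per cell. At r = 0.3, 0.5 and 0.7:
- no gate, six nulls: 25.1, 20.2 and 16.9%;
- gated, six nulls: 4.5, 3.9 and 3.1%;
- gated, one effect of 0.8 SD: 21.2, 18.5 and 15.1%, with the gate open in 98.7 to 100% of trials.

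These agree with the steps above, so the covariates do not change the picture.

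**Step 6. Holm across the six.** With six nulls the risk is 4.9% (r = 0), 4.1% (0.5), 2.1% (0.9) and 1.7% (0.95). With one to five large real effects the highest simulated rate is 5.1%, which is 5% within simulation error. The first threshold is 0.05/6 = 0.0083.

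**The case against.** **The order of the tests may imply a gate.** An omnibus test followed by single-outcome tests is compatible with a protective scheme. Under that reading the risk with six true nulls is below 5%, where the ungated calculation gives up to 26.5%. This stands as far as it goes. The SAP does not state the condition, however, and step 3 shows that a gate would not protect single-outcome claims once a moderate effect exists.

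**26.5% is a boundary.** It needs uncorrelated statistics, no gate and no effect on any outcome. The six measures come from the same participants, so some correlation is likely. This also stands, and the whole range should be quoted. The risk is still 8.9% at r = 0.95.

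**A gate protects only if all six outcomes are null.** A reader might infer this, but it is too absolute. The risk is also at or below 5% when at most one outcome is null, and when real effects are too small to open the gate (z-shift 0.5 in step 3). The 22.6, 18.3 and 14.8% figures are large-effect limits and do not apply to every real effect.

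**The SAP fails because it names no primary outcome or significance level.** A reader might infer this too. The protocol is not shown and commonly carries both, so their absence here is no fault. A primary outcome would settle the main claim and leave five outcomes without a rule in this plan. Whether secondary outcomes are adjusted or simply labelled exploratory is partly convention, but the plan should say which.

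**Conclusion.** The point holds as a defect in the stated test sequence. As written, the MANCOVA does not control the false-positive risk of the six single-outcome ANCOVAs, and nothing else in the SAP does.

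Without a gate and with six true nulls, the risk runs from 8.9% to 26.5% over r = 0.95 to 0. With a gate, it exceeds 5% when real effects are moderate or large and two or more outcomes are null. With one real effect it is about 13% at a z-shift of 2, and higher as the effect grows.

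The level of 0.05, the common correlation and the effect sizes are assumptions, so these figures illustrate the size of the problem and do not estimate this trial's error rate. They do not count the repeat in the imputed data or the within-group t-tests. They also do not show that any particular reported result is false. The change should be made, with medium confidence, because the unseen protocol could narrow the point.

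**What to change.** 1. Apply Holm's step-down adjustment across the six ANCOVA p-values in the completer analysis. Use the same rule in the imputed sensitivity analysis, for consistency.
2. If the protocol names a primary outcome, test it first at its stated level. Apply Holm to the other five only if it is significant; otherwise report those five as exploratory.
3. Report raw and adjusted p-values side by side.
4. Label the adjustment post hoc. The SAP describes finished work ("All analyses were carried out in SPSS V29.0.1.1"), so a rule chosen now cannot restore pre-specification.
5. Describe the MANCOVA as a global test that does not protect individual outcomes.
6. State that the within-group paired t-tests lie outside this adjustment and are not used for between-group claims.

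If no adjustment is made, the minimum is to label the six ANCOVAs as unadjusted and exploratory.

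The cost is small: a calculation on existing p-values and revised results tables, with no new data or models. The downside is that, with Holm over six at 0.05, the smallest p-value must be at or below 0.0083, so marginal outcomes may lose significance.

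### Clinically significant change is defined by position against a cut-off, with no minimum change, no stated visit and no between-group comparison, so fluctuation can count as change

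*SAP*

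**What the plan says.** The SAP is a single section, Statistical Analysis Plan. Its last paragraph defines clinically significant change in one sentence: "we used Jacobsen and Truax's Criterion B (falling within 2 SD of the healthy mean"). The choice is justified by strictness, "which is more conservative than Criterion A (falling 2 SD below the pathological mean"). The sentence cites a source for the criteria but adds no other condition from it. It names no scale, norm, cut-off value or visit, and no required baseline status.

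The between-group analyses come earlier in the section. They "examine between group effects at post treatment (8 weeks), controlling for baseline levels of the dependent variables": first a MANCOVA on all six scales, then, "We then ran a series of ANCOVAs predicting each of the outcome measures individually at post-treatment from condition controlling for that measure's baseline value". Post-test is described as "the only time point at which between group comparisons were possible". Paired t-tests are also used "to examine maintenance of gains from post CBT treatment to 3- and 6-months follow-up", so there are several visits to which the criterion might apply.

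**The concern.** The label is clinically significant change, but the rule describes an end position. A participant slightly outside the healthy range at baseline can drift slightly inside it through measurement error or ordinary symptom variation, and then meets the rule. Nothing in the definition separates that participant from one who improved substantially.

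A comparison between groups would show how many crossings also occur under the comparator, but none is stated for these proportions: every named between-group test uses the continuous scores. A percentage per group therefore mixes treatment effect, natural course and noise. The two gaps reinforce each other, because the definition lets noise in and no contrast is stated that would take it out.

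**Working it through.** **Inputs.** The SAP supplies the rule (within 2 SD of the healthy mean) and the 8-week post-treatment visit. It gives no healthy means, SDs, cut-off values or reliabilities, so there is no planned figure to reproduce. Everything below is an illustration under stated assumptions.

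**Assumptions.** Scores are oriented so that higher is worse and are normal with SD 1 at both visits. There is no true change. The correlation between baseline and 8 weeks is r = 0.6 to 0.9. The sample mean lies m SD beyond the cut-off (placed at 0). Only participants outside the cut-off at baseline are counted, which is kinder to the rule than its wording.

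**Noise crossing.** With X the baseline score and Y the 8-week score:

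P(cross) = P(X > 0, Y ≤ 0) / P(X > 0).

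At m = 0 this reduces to 1/2 − arcsin(r)/π. For r = 0.7 that is 0.5 − 0.7754/3.1416 = 0.253, which agrees with simulation (25.3%).

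**Reliable change.** The added condition is X − Y > 1.96 × √(2(1 − r)) SD. The threshold is 1.96 × √0.8 = 1.75 SD at r = 0.6, 1.96 × √0.4 = 1.24 SD at r = 0.8, and 1.96 × √0.2 = 0.88 SD at r = 0.9.

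| m (SD beyond cut-off) | Already inside at baseline | Noise crossing, r = 0.9 | r = 0.8 | r = 0.6 | With reliable change, r = 0.9 to 0.6 |
|---|---|---|---|---|---|
| 0.5 | 31% | 9.1% | 13.0% | 18.7% | 1.3-2.5% |
| 1 | 16% | 5.1% | 7.2% | 10.2% | 0.8-1.5% |
| 2 | 2.3% | 1.0% | 1.3% | 1.8% | 0.15-0.4% |
| 2.5 | 0.6% | 0.3% | 0.4% | 0.5% | 0.05-0.14% |

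The second column is 1 − Φ(m). Because the SAP states no baseline condition, these participants could count as well.

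**Which row applies.** Let the healthy and patient means be D SD apart, with equal SDs. Criterion B then lies D − 2 SD from the patient mean and Criterion A lies 2 SD from it. B is the stricter only if D − 2 > 2, that is D > 4 and m > 2. If the SAP's remark on strictness is right for these scales, noise crossing is below about 2%. The 5-19% rows apply only where that remark fails. Without norms the SAP does not settle which.

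**Natural course.** Suppose both groups improve by 0.3 SD with no app effect, at m = 1. Then 12.1% (r = 0.9) to 17.5% (r = 0.6) cross in each group, or 3.4-3.6% with the reliable-change condition. This is real improvement shared by both groups, not noise. The condition reduces it but only a between-group contrast removes it.

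**Choice of reliability.** The last column takes the threshold from the same r that governs 8-week fluctuation. If the threshold instead uses a reliability of 0.9 (0.88 SD) while the 8-week correlation is 0.6, crossing with the condition is 6.4% at m = 1 rather than 1.5%, and 11.2% at m = 0.5 rather than 2.5%. With an 8-week correlation of 0.8 it is 2.8% rather than 1.1%, and 4.9% rather than 1.8%.

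**The case against.** The strongest reply is that the measure is supplementary. It stands beside the effect sizes, no test or efficacy conclusion is attached to it, and the treatment effect is assessed by baseline-adjusted models on continuous scores. That stands, and those models are unaffected by this point.

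Three stronger readings are tempting but unsupported:

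- A reader might infer that the criterion is applied at 8 weeks. The sentence names no visit; 8 weeks belongs to the MANCOVA and ANCOVA text.
- A reader might infer that fluctuation is counted as recovery on a large scale. The SAP does not use that word for this measure, and the frequency cannot be derived from it. On the SAP's own view that Criterion B is the stricter, with equal SDs, it would be under 2%.
- A reader might infer that the app is wrongly credited with noise. Noise crossings arise in both groups, and the SAP draws no efficacy conclusion from these percentages.

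The absence of a reliable-change condition and of a group comparison is also read from silence, in a sentence that cites a source not seen here. That is a fair caution. However, the SAP takes only Criterion B from that source, and someone applying the text as written would apply nothing more.

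Finally, a 95% reliable-change threshold has a price: it excludes participants who improve genuinely but modestly and end in the healthy range. That is a reason to report the end-state proportion alongside, not to let it stand as the definition of change.

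**Conclusion.** The point holds in a limited form. The rule is one of position only, is tied to no visit, and has no stated between-group comparison. Fluctuation without true change can therefore count as clinically significant change, and the percentages cannot be read against the comparator.

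The size cannot be determined from the SAP. Under the assumptions above it runs from about one in five of those outside the cut-off at baseline to well under 1%, depending mainly on how far the sample lies from the healthy range. The case for repair rests on the definition and the missing contrast, not on any one of these figures.

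**What to change.** - **Definition.** Name the scales, the source of the healthy norms, the cut-off values and the visit. Count a participant as clinically significantly changed only if the score moves from outside to inside the cut-off and the change exceeds 1.96 × the standard error of the difference for that scale.
- **Reliability.** Calculate that standard error from a test-retest reliability over an interval close to 8 weeks. Internal consistency is not a substitute, because it understates fluctuation over that period.
- **End state.** Report the proportion within the healthy range alongside, labelled as descriptive.
- **Contrast.** At post-treatment, give the between-group risk difference with a 95% CI, adjusted for the baseline score. Base any statement about the app's clinical significance on it.

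The cost is a few lines of SAP text, a short extra analysis of scores the plan already uses, and one suitable reliability per scale. The reported percentages will be lower, and some participants with genuine but smaller change will not count.
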